5.3.2 Secondary Surgical Interventions

Descriptive summaries (counts, percentages, and two-sided 95% exact confidence intervals) of secondary surgical interventions (SSIs) will for presented for each treatment group and the difference between the groups, separately for first and second implanted eyes in each of the following categories:

1. Related to IOL – due to optical properties
2. Related to IOL – not due to optical properties
3. Unrelated to IOL
4. Overall

A listing of all SSIs will be also be presented.

[REDACTED]

[REDACTED]
[REDACTED]
[REDACTED]

5.3.3 Device Deficiencies

The applicable definition of a device deficiency is in the study protocol. The number and percentage of all device deficiencies will be tabulated with a breakdown by treatment group and implanted eye. A listing of all device deficiencies will also be provided.

5.3.4 Intraocular Pressure

Intraocular pressure (IOP) measurements will be recorded in mmHg and rounded to the nearest whole mmHg. All analyses will be presented by treatment group, separately for first and second operative eyes.

Descriptive summaries (n, mean, median, standard deviation, minimum, maximum and 95% (two-sided) confidence interval) of observed values and change from baseline values will be presented at each study visit by treatment group, separately for first and second implanted eyes.

A listing will be provided which presents all eyes with an increase or decrease in IOP of more than 10 mmHg at any visit compared to the same eye at baseline. The listing will include the following variables: treatment, site, subject, age, sex, eye, visit, days from surgery, baseline value, value at the visit, and a change from baseline value.

5.3.5 Slit Lamp Examination Findings

For each slit-lamp parameter, number and percentages of eyes that experience abnormality at any post-operative visit will be presented by treatment group, separately for first and second implanted eyes.

A listing will be provided which presents all eyes with an abnormality in any slit-lamp parameter at any post bilateral implantation visit. The listing will include all slit-lamp data from all visits with the following variables: treatment, site, subject, age, sex, eye, parameter, visit, baseline value, and value at the visit.

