10.2.3 Visit 1: Postoperative for 1st Eye (1-2 days after Visit 00)

1. Record changes in **medical/ocular history** and **concomitant medications** for ocular and non-ocular conditions.
2. Perform **slit-lamp examination** of the anterior segment. *Note that only unmasked site staff can perform slit-lamp exam.*
3. Record **IOL observations**, if any.
4. Record **lens decentration and/or tilt**, if applicable.

5. Record **subjective posterior capsule opacification** and information for any **posterior capsulotomy** that has occurred since surgery, if applicable for operative eye.
6. Perform **tonometry** to measure the intraocular pressure.
7. Record **secondary surgical interventions** that have occurred since surgery, if applicable.
8. Record any **adverse events**.
9. Record any **device deficiencies**, if applicable.

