2.3 Safety Analysis Set

The Safety Analysis Set (SAF) will include all eyes with attempted implantation (successful or aborted after contact with the eye). The SAF will be the primary set for all safety analyses.

All analyses at the eye-level endpoints (such as ocular adverse events) will be presented separately for first implanted eyes and second implanted eyes. While analyses at the subject-level endpoints (such as non-ocular adverse events) will be based on the subjects.

Safety analyses will be conducted using the safety analysis set on a treatment-emergent basis. For treatment-emergent safety analyses, eyes will be categorized under the actual IOL implanted (or attempted to implant).

3 Subject Characteristics and Study Conduct Summaries

Subject characteristics and study conduct summaries include tables and listings such as a subject disposition table, demographics and baseline characteristics tables (including age, gender, race), listing of treatment assignments by site, summary of screen failures by reason, and listing of subjects/eyes excluded from the analysis sets including reasons.

All summary statistics will be based on the type of variable. For categorical variables (eg, sex, race), summary statistics will include sample size, number in category, and % in each category. For continuous variables (eg, age, axial length), number of subjects/eyes, mean, median, standard deviation, minimum and maximum will be reported. Tables will be presented by treatment and overall.

[REDACTED]

[REDACTED]

[REDACTED]

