5.3 Statistical Methods for Safety Analyses

The focus of the safety analysis will be a comprehensive descriptive assessment of safety endpoints listed in Section 5.1. Except otherwise stated, the analysis set for all safety analyses is the safety analysis set as defined in Section 2.3. Baseline will be defined as the last measurement prior to exposure to investigational product, except otherwise stated.

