5.3.6 Dilated Fundus Exam Findings

For each dilated fundus parameter, number and percentages of eyes that experience abnormality at any post-operative scheduled and unscheduled visit will be presented by treatment group, separately for first and second implanted eyes.

A listing will be provided which presents all eyes with abnormality in any fundus parameter at any post-operative visit. The listing will include the following variables: treatment, site, subject, age, sex, visit, days from surgery, eye, baseline value and value at the visit.

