5.3.7 IOL Observations

IOL observations will be summarized by treatment group using descriptive statistics, including frequency and percent of eyes, by treatment group, separately for first and second implanted eyes, at each scheduled and unscheduled visit where the data were collected.

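### The slit-lamp and fundus tables (SAP 5.3.5, 5.3.6) count any postoperative abnormality without reference to the same eye's baseline, so unchanged pre-existing findings are tabulated under the lens

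*SAP*

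**What the plan says.** For slit-lamp findings, SAP 5.3.5 plans one cumulative figure per parameter, given separately for first and second implanted eyes: "number and percentages of eyes that experience abnormality at any post-operative visit will be presented by treatment group". For the fundus, SAP 5.3.6 plans the "number and percentages of eyes that experience abnormality at any post-operative scheduled and unscheduled visit", with the same split by eye.

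Two general rules sit above these sections. SAP 2.3 states: "Safety analyses will be conducted using the safety analysis set on a treatment-emergent basis". SAP 5.3 states: "Baseline will be defined as the last measurement prior to exposure to investigational product, except otherwise stated". For slit-lamp and fundus findings that baseline is normally the Visit 0 examination, the only preoperative one in the schedule (Protocol Table 3-1, SAP Table 10-1).

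Both sections also plan listings that print the baseline value beside the visit value. On the slit-lamp listing, SAP 5.3.5 says: "The listing will include all slit-lamp data from all visits with the following variables".

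**The concern.** Under the wording of 5.3.5 and 5.3.6, an eye that was abnormal in a parameter at Visit 0 and is unchanged afterwards is counted as an eye with a postoperative abnormality. That finding did not emerge under treatment. No visible text says whether the general rule in 2.3 or the specific table sentence governs, so two programmers could produce different tables from the same SAP.

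Slit-lamp and fundus findings are named safety endpoints (Protocol 6.4, SAP 5.1), and the study is intended for publication (Protocol 5.2). A percentage that mixes background findings with new ones makes a real difference between lenses look smaller. It also lets a chance imbalance in pre-existing findings look like a lens effect.

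**Working it through.** **1. Set the rules side by side.**

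| SAP section | Same-eye baseline used in the summary? | Shown by visit? |
|---|---|---|
| 2.3, general rule | Yes, by its treatment-emergent basis | Not addressed |
| 5.3.4 IOP | Yes, change from baseline | Yes |
| 5.3.5 slit-lamp table | No | No, any postoperative visit |
| 5.3.6 fundus table | No | No, any postoperative visit |
| 5.3.7 IOL observations, 5.3.9 PCO | No preoperative counterpart | Yes, "at each scheduled and unscheduled visit where the data were collected" |

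Only the missing baseline condition departs from 2.3. A finding absent before surgery, seen at Day 1-2 and then gone, is itself treatment-emergent.

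**2. Eyes per lens.** Protocol section 8 gives 180 completing, 198 randomized and 218 enrolled. These reproduce as 180 × 1.1 = 198 and 198 × 1.1 = 217.8, rounded to 218. With 1:1:1 allocation, 198 / 3 = 66 subjects per lens. That is at most about 66 first eyes and 66 second eyes per lens in the slit-lamp table. It is not the number examined for the fundus table, because no postoperative fundus examination is scheduled.

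**3. Dilution.** The documents give no rate of pre-existing or new findings, so all rates here are assumptions. Let b be the share of eyes with a background finding in one parameter, equal across lenses and independent of the lens. Let t be the incidence of new findings.

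- Tabulated rate = b + (1 - b) × t
- Between-lens difference = (1 - b) × (t₁ - t₂)

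Take t = 2% against 12%, a true difference of 10 points. The 95% half-width is 1.96 × √[p₁(1 - p₁)/66 + p₂(1 - p₂)/66].

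| b | Tabulated rates | Difference (points) | 95% half-width (points) |
|---|---|---|---|
| 0 | 2.0% vs 12.0% | 10.0 | 8.5 |
| 0.05 | 6.9% vs 16.4% | 9.5 | 10.8 |
| 0.1 | 11.8% vs 20.8% | 9.0 | 12.5 |
| 0.3 | 31.4% vs 38.4% | 7.0 | 16.2 |
| 0.5 | 51.0% vs 56.0% | 5.0 | 17.0 |

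For example, at b = 0.1 the rates are 0.1 + 0.9 × 0.02 = 0.118 and 0.1 + 0.9 × 0.12 = 0.208. The b = 0 row is what a new-or-worsened count would show if it removed the background fully.

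**4. Noise.** If 20% of eyes carry a pre-existing finding in a parameter, the chance difference in prevalence between two lenses has standard deviation √(2 × 0.2 × 0.8 / 66) = 0.070, or about 7 points. Its expected value under randomization is zero.

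**The case against.** The case against has real weight, and most of it limits the size of the point.

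- **The baseline is not discarded.** SAP 2.3 sets a general rule, SAP 5.3 defines the baseline, and both listings print it. The SAP is to be read with table shells that are not public, and parts of its text are blacked out. This stands as a caution. But the listings go eye by eye and give no count per lens, and the visible table sentences state a counting rule that 2.3 would not give.
- **Adverse events offer another route.** Protocol 11.2 requires a clinically relevant untoward change in a protocol parameter to be reported as an adverse event. Protocol 11.3 keeps conditions present before consent out of that count, and SAP 5.3.1 tabulates ocular events by treatment. This stands: the two tables are not the only by-lens view of important new findings. They remain the visible planned summary of the examination findings themselves, including changes not judged clinically relevant.
- **Safety is descriptive and randomized.** SAP 5.2 has no safety hypotheses. This stands, so no formal decision rests on these percentages.

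A reader might go further and infer that background and early findings overwhelm any lens difference. The documents give no background rates. At b of 0.05 to 0.1 a 10-point difference falls only to 9.5 or 9.0 points. The share also has to arise within a single parameter, since the tables are per parameter. Nor can the amount of pre-existing pathology be judged from Protocol 8.2, where the visible exclusion on disease expected to reduce vision is cut off by redaction.

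A reader might also infer that pooling early and late visits breaks SAP 2.3. It does not, since a new transient finding is treatment-emergent and an ever-abnormal incidence is a legitimate conservative summary. The early-visit argument has no place for the fundus at all: the schedules show that examination at Visit 0 and then only as needed at unscheduled visits.

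**Conclusion.** The point holds as a mismatch between the two table definitions and the SAP's own general rules. Sections 5.3.5 and 5.3.6 count unchanged pre-existing abnormalities under the lens, while 2.3 calls for a treatment-emergent basis and 5.3 supplies the baseline needed to apply it.

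The consequence is dilution and noise, not expected bias. A between-lens difference is multiplied by (1-b), so 10 points become 9, 7 or 5 at b = 0.1, 0.3 or 0.5. This rests on an assumed background that is equal across lenses and independent of the lens, and the documents do not say which value of b is realistic. It also assumes that no blacked-out text or table shell already restricts the count. The correction is modest but worth making, because it concerns named safety endpoints and costs little.

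**What to change.** In SAP 5.3.5 and 5.3.6, define the main tabulated quantity as the number and percentage of eyes with a new or worsened finding compared with the same eye's baseline, by treatment group and separately for first and second eyes. Keep the any-abnormality count as a secondary row if wanted.

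For slit-lamp only, a by-visit display like those in 5.3.7 and 5.3.9 is an optional addition. It would let a reader tell an early transient finding, such as one seen only at "Visit 1: Postoperative for 1st Eye (1-2 days after Visit 00"), from one that persists. SAP 2.3 does not require it.

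The cost is SAP wording and a few table rows. Baseline and visit values are already collected and already planned for the listings, so no visit or procedure is added.

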5.3.6 Dilated Fundus Exam Findings

For each dilated fundus parameter, number and percentages of eyes that experience abnormality at any post-operative scheduled and unscheduled visit will be presented by treatment group, separately for first and second implanted eyes.

A listing will be provided which presents all eyes with abnormality in any fundus parameter at any post-operative visit. The listing will include the following variables: treatment, site, subject, age, sex, visit, days from surgery, eye, baseline value and value at the visit.

5.3.7 IOL Observations

IOL observations will be summarized by treatment group using descriptive statistics, including frequency and percent of eyes, by treatment group, separately for first and second implanted eyes, at each scheduled and unscheduled visit where the data were collected.

5.3.8 IOL Position Change (Tilt/Decentration)

Descriptive statistics (number and percentages) on eyes with a change from last visit in IOL position category (Tilted, Decentered) will be presented by treatment group, separately for first and second implanted eyes.

In addition, a listing of eyes with IOL position change will be provided. The listing will include the following variables: treatment, site, subject, age, sex, visit, days from surgery, eye and amount of tilting or decentration.

5.3.9 Subjective Posterior Capsule Opacification (PCO) Assessment

Subjective posterior capsule opacification will be summarized using descriptive statistics, including number and percent of eyes, at each scheduled and unscheduled visit where the data were collected, by treatment group, separately for first and second implanted eyes.

A listing of eyes with clinically significant posterior capsule opacification, clinically significant posterior capsule opacification requiring YAG or posterior capsulotomy will be presented which includes the posterior capsule opacification or capsulotomy values at all visits. The listing will include the following variables: treatment, site, subject, age, sex, visit, days from surgery, eye and posterior capsule opacification or capsulotomy value at the visit.

5.3.10 Posterior Capsulotomy

An incidence table of eyes with posterior capsulotomy will be tabulated with a breakdown by treatment group, separately for first and second implanted eyes.

[figure not shown]
5.3.11 Intraoperative Surgical Problems

Descriptive statistics (numbers and percentages) on eyes with surgical problems will be presented, separately for first and second implanted eyes.

In addition, a listing of subjects with surgical problems will be provided. The listing will include the following variables: treatment, site, subject, age, sex, eye, and description of surgical problem.

[figure not shown]
[figure not shown]
5.3.12 Other Procedures at Surgery (Combined and/or Additional)

A listing of all other surgical procedures will be provided. The listing will include the following variables: treatment, site, subject, age, sex, eye, and type of other surgical procedure.

7 Sample Size and Power Calculations

Approximately 218 subjects will be enrolled to achieve 180 subjects who complete the study.

10 Appendix

Table 10–1 Schedule of Study Procedures and Assessments

Visit	Visit 0	Visit 00	Visit 1	Visit 2	Visit 00A	Visit 1A	Visit 2A	Visit 3A	Visit 4A ¹	Visit 5A	Unscheduled visit
Eye	Both Eyes	1 st Eye	1 st Eye	1 st Eye	2 nd Eye	2 nd Eye	2 nd Eye	Both Eyes	Both Eyes	Both Eyes	N/A
Day Number	Day -28 to 0	Day 0	Day 1-2 Post Visit 00	Day 7-14 Post Visit 00	Day 7-21 Post Visit 00	Day 1-2 Post Visit 00A	Day 7-14 Post Visit 00A	Day 30-60 Post Visit 00A	Day 70-100 Post Visit 00A	Day 120-180 Post Visit 00A	N/A
General Assessments and Procedures											
Informed Consent	X										
Demographics	X										
Medical History	X										
Concomitant Medications	X	X	X	X	X	X	X	X	X	X	X
Inclusion/Exclusion	X										
Urine Pregnancy Test ²	X										
Ophthalmic Assessments											
Questionnaires											
• QUID (for visual disturbance)	X							X	X	X	
■ [REDACTED]	■							■	■		
■ [REDACTED]								■	■		

Visit	Visit 0	Visit 00	Visit 1	Visit 2	Visit 00A	Visit 1A	Visit 2A	Visit 3A	Visit 4A ¹	Visit 5A	Unscheduled visit
Eye	Both Eyes	1 st Eye	1 st Eye	1 st Eye	2 nd Eye	2 nd Eye	2 nd Eye	Both Eyes	Both Eyes	Both Eyes	N/A
Day Number	Day -28 to 0	Day 0	Day 1-2 Post Visit 00	Day 7-14 Post Visit 00	Day 7-21 Post Visit 00	Day 1-2 Post Visit 00A	Day 7-14 Post Visit 00A	Day 30-60 Post Visit 00A	Day 70-100 Post Visit 00A	Day 120-180 Post Visit 00A	N/A
██████████ ██████████	■							■	■		
Biometry (collect all available measurements including ACD, AL, keratometry, corneal thickness, crystalline lens thickness, white-to-white)	X								X		
Manifest Refraction	X			X			X	X	X	X	(✓)
██████████											
■ ██████████									■		
■ ██████████	■			■			■	■	■	■	■
■ ██████████									■		
██████████											
■ ██████████									■		
■ ██████████									■		
██████████											

Visit	Visit 0	Visit 00	Visit 1	Visit 2	Visit 00A	Visit 1A	Visit 2A	Visit 3A	Visit 4A ¹	Visit 5A	Unscheduled visit
Eye	Both Eyes	1 st Eye	1 st Eye	1 st Eye	2 nd Eye	2 nd Eye	2 nd Eye	Both Eyes	Both Eyes	Both Eyes	N/A
Day Number	Day -28 to 0	Day 0	Day 1-2 Post Visit 00	Day 7-14 Post Visit 00	Day 7-21 Post Visit 00	Day 1-2 Post Visit 00A	Day 7-14 Post Visit 00A	Day 30-60 Post Visit 00A	Day 70-100 Post Visit 00A	Day 120-180 Post Visit 00A	N/A
█ ██████████									█		
█ ██████████									█		
██████████									█		
██████████ ██████████									█		
██████████ ██████████									█		
██████████									█		
██████ ███ ████████										█	
Slit-lamp Examination											
• Observations	X		U	U		U	U	U	U	U	U(✓)
• IOL Position change (tilt/decentration)			U	U		U	U	U	U	U	U(✓)
IOP	X		X	X		X	X	X	X	X	(✓)
Dilated Fundus Examination	X										U(✓)

Visit	Visit 0	Visit 00	Visit 1	Visit 2	Visit 00A	Visit 1A	Visit 2A	Visit 3A	Visit 4A ¹	Visit 5A	Unscheduled visit
Eye	Both Eyes	1 st Eye	1 st Eye	1 st Eye	2 nd Eye	2 nd Eye	2 nd Eye	Both Eyes	Both Eyes	Both Eyes	N/A
Day Number	Day -28 to 0	Day 0	Day 1-2 Post Visit 00	Day 7-14 Post Visit 00	Day 7-21 Post Visit 00	Day 1-2 Post Visit 00A	Day 7-14 Post Visit 00A	Day 30-60 Post Visit 00A	Day 70-100 Post Visit 00A	Day 120-180 Post Visit 00A	N/A
Surgical Procedures & Assessments											
Determination of 1 st Operative Eye	X										
IOL Power Calculations (all 3 IOLs)	X										
████████████████████ ██████████ ████████████████████	■										
Randomization ⁴		U									
Treatment		U			U						
IOL Information (Power, Model, SN)		U			U						
Problems During Surgery		U			U						
Other Surgical Procedures		U			U						
PCO and Posterior Capsulotomy			U	U		U	U	U	U	U	U(✓)
Adverse Events & Device Deficiencies											

Visit	Visit 0	Visit 00	Visit 1	Visit 2	Visit 00A	Visit 1A	Visit 2A	Visit 3A	Visit 4A ¹	Visit 5A	Unscheduled visit	
Eye	Both Eyes	1 st Eye	1 st Eye	1 st Eye	2 nd Eye	2 nd Eye	2 nd Eye	Both Eyes	Both Eyes	Both Eyes	N/A	
Day Number	Day -28 to 0	Day 0	Day 1-2 Post Visit 00	Day 7-14 Post Visit 00	Day 7-21 Post Visit 00	Day 1-2 Post Visit 00A	Day 7-14 Post Visit 00A	Day 30-60 Post Visit 00A	Day 70-100 Post Visit 00A	Day 120-180 Post Visit 00A	N/A	
AEs ⁴	X	X	X	X	X	X	X	X	X	X	X	
Device Deficiencies		X	X	X	X	X	X	X	X	X	X	
Other												
Exit Form	(✓)	(✓)	(✓)	(✓)	(✓)	(✓)	(✓)	(✓)	(✓)	(✓)	X	(✓)

(✓) assessment performed as necessary

[figure not shown]
█ [REDACTED]

█ [REDACTED]

█ [REDACTED]

4. Collected from time of consent onward.

Signature Page for V-CLN-0006740 v3.0

Signature Page for V-CLN-0006740 v3.0
